#### C.2.4 Dietary Intake Across the 5 Sites

Dietary intake data have been collected in each of our 5 study sites. In the US and Jamaica our group has significant experience in the collection and analysis of 24-hour recall and FFQ data with analysis completed using the Nutrient Data System for Research (NDSR) [139-141]. In Nigeria, until very recently a nutrient database specific to Nigerian foods was not available and thus dietary analysis was limited to foods and food patterns; a site-specific database is now available and nutrient analyses will be conducted on previously collected 24-hour recalls [142]. In the Seychelles, our co-investigator has been working with dietitians at the Ministry of Health to create and validate a nutrient database specific to Seychelles using the UK system, WISP (personal communication, [name] & [name]) [143, 144]. In South Africa, our new co-investigator [name], has extensive experience with dietary intake measurement at the national level [145] and developed a system with colleagues at the MRC to improve estimation of portion sizes, the Dietary Assessment and Education Kit (DAEK); there is a South Africa-specific nutrient database available.

In Table 4, the most frequently consumed foods, assessed by repeated, multiple pass 24-hour dietary recalls, are presented for each of the 5 study sites.

**Table 4. Most Frequently Reported Foods and Energy Intake by Site – 24-hr Dietary Recall Data**

	Jamaica (n = 270)	Maywood (n = 197)	Nigeria (n = 125)	Seychelles (n = 243)	South Africa (n = 563)
Instrument	24-hr recall	24-hr recall	24-hr recall	24-hr recall	24-hr recall
Most frequent	Brown bread	Soft drinks	White bread	Rice	Sugar
#2	Cheese	Chicken	Pepper stew	Sugar	Maize porridge
#3	Rice	Potatoes	Cow peas	Whole milk	Bread
#4	Beans	White bread	Vegs-greens	White bread	Potatoes
#5	Chicken	Beef	Beef	Tea	Milk
Energy intake (kcal/d)	2130	2520	2475*	2150	1860
Fat (% kcal)	31%	41 %	26%*	26%	26%

\* estimated from sub-sample of recalls

It is of interest to note – illustrating the rapid environmental change developing countries are undergoing - that in rural Nigeria 8 years ago white bread accounted for only 2.3% of the foods, compared to 24.9% in 2007; cassava, the most frequently reported food in 1999, was not in the top 5 in 2007 (unpublished observation, [name]). In Seychelles, there was a 17% decrease in the consumption of fresh fish and concomitant increase in dairy and red meat intake between 1993 and 2003 (personal communication, [name]).

## D. EXPERIMENTAL DESIGN AND METHODS

### D.1 Project Overview

#### D.1.1 Participant Recruitment and Baseline Exam

Population-based samples, ages 25-45, will be drawn from communities in 5 countries: Nigeria, Seychelles, South Africa, Jamaica and the US; 500 per site, 2500 total. Based on our overall experience with

longitudinal studies, we experienced 2% annual attrition in Nigeria and 10% in the US site, we anticipate no more than 20% attrition by the 24-month examination, resulting in a final 'N' of at least 400 per site (Table 5).

#### D.1.2 Hypotheses to be Tested

[figure not shown]
- 1) PA is negatively related to percent body fat in the study populations at baseline, independent of dietary intake.
- 2) PA is negatively related to change in body weight during follow-up, independent of dietary intake.
- 3) Mean levels of AEE are negatively related to mean levels of obesity/relative weight among the populations.
- 4) Adipocytokines and hormones influence weight regulation and insulin sensitivity and interact with AEE.

**Table 5. Proposed Study Measures**

	Baseline (N)	12-Mo Follow-Up (N)	24-Mo Follow-Up (N)	Use of Data
Physical Activity				
Accelerometer	2500		2500	Exposure
DLW	375			Concordance, exposure
Questionnaire	2500			Exposures
Body Composition				
BIA	2500		2500	Outcome: baseline & change
Isotope Dilution	500		500	Calibrate BIA change data
Dietary Intake	2500			Covariate
Anthropometrics	2500	2500	2500	Outcome: baseline & change
Blood pressure	2500			Outcome
Adipocytokines/Hormones	2500			Outcome

#### D.2 Study Organization and Time Line

The Department of Preventive Medicine in Chicago will serve as the coordinating center. During the first 6 months, a detailed protocol will be finalized, and staff from all sites will come to Chicago for a group training session. Staff at each site will be responsible for translating and back translating all patient materials, including consent forms and questionnaires, into the local language. These materials will be piloted on 10 people at each site in the first 6 months. The DLW protocol and concurrent accelerometer baseline protocol for the 75 selected individuals/site will be conducted between month 6 and 18 in all sites. The baseline accelerometer protocol for the additional 425 participants/site will be carried out over the course of a year beginning at 6 months. The follow-up examinations will begin at 1.5 years, for a 2.0-year period. As discussed previously, these will involve measuring weight for all 500 participants/site at 12 and 24 months of follow-up with accelerometer and body composition measurements at 24 months of follow-up. Laboratory analyses of the DLW samples will commence at approximately year 1. Deuterium analyses for body composition assessments will be conducted in years 1 and 4. Fasting hormone and glucose samples will be collected at the baseline examination and stored at -80C; the samples will be analyzed in year 4. Primary data analysis and report writing will be conducted in year 4. Figure 6 shows a graphical representation of the previously discussed timeline. A detailed timeline can be found in Appendix B.

**Figure 6. Time Line**

Communication between investigators will be maintained by monthly conference calls coordinated by the Loyola group. The project coordinator and/or PI will travel to each site annually for site visits with staff and co-investigators.

### D.3 Clinic Overview

#### D.3.1 Clinic Examinations and Data Acquisition

Each of the sites has been conducting community-based CV research and has community-centered clinics from which the present study will be based (see below). For participants enrolled in the DLW/deuterium protocol, the initial clinic examination will last approximately 4 hours. They will return to the clinic, or be visited by a staff member at their home, on day 5 ( $\pm 1$  day) to provide a midpoint urine sample and to ensure the accelerometer is comfortable and being worn properly. They will be asked to return to the clinic on day 9 ( $\pm 1$  day) to provide a final urine sample and have the accelerometer removed. For the participants enrolled in the accelerometer protocol, the clinic examination will last approximately 1 hour. A staff member will check on each participant on day 2 to ensure that the accelerometer is comfortable and being worn properly, and the participant will return on day 9 to return the accelerometer and have a final body weight measurement taken.

All anthropometric measurements, BP, and blood collection will be made at the initial clinic examination, with participants fasted from the evening prior. Demographic data and medical history, including age, gender, season, birth place, occupation, education, tobacco use, alcohol use and pregnancy history, will also be collected at this time. At 12 and 24 months after the baseline examination, all participants will be recontacted for follow-up clinic examinations.

#### D.3.2 Sampling Procedures

In each of the 5 sites, 75 individuals aged 25-45 years will be recruited for the DLW protocol and 425 will be recruited for the accelerometer protocol, with equal numbers of men and women. We will exclude individuals with obvious chronic or infectious diseases (including active malaria), pregnant or lactating women, and HIV positive individuals (see D.3.3 for HIV testing procedures). Any individual that has a condition preventing normal AEE will also be excluded from our study. Population-based surveys have been carried out in each of the sites; the sampling procedures used previously will be employed in the present study. These study sites were chosen because mean BMIs and prevalence of obesity span the healthy physiological range.

Jamaica – Spanish Town is an urban area 25 km from the center of Kingston. Once the capital of colonial Jamaica, Spanish Town is an established community with a population of 92,000 in 1991; about 45,000 individuals are between the ages of 25 and 74. A community-based study of hypertension and diabetes (n=3500) has been completed [123]. Districts were randomly sampled; beginning from a fixed point in each district (e.g., the north-west corner), door-to-door screening took place. Examinations will be carried out in the local health clinic and specimens taken immediately to the Univ. of the West Indies for processing.

US – Maywood is an African-American working class community adjacent to the western border of Chicago, Illinois. Approximately 3,500 participants have been examined in our clinic since 1991 for both observational and interventional studies [123]. Participation rates for observational components of these studies have been 60% or greater. Project staff are residents of the community and conduct all recruitment and home visits. We have now contacted individuals on approximately two thirds of the blocks in Maywood and are well known to the community. The Department clinic is on campus, within walking distance of most neighborhoods and is well known to local residents. We will also recruit from the adjoining west side of Chicago.

Nigeria – Developed in 1965 as a teaching site for the University College Hospital (UCH), University of Ibadan, Igbo-Ora is a rural community with a population of 50,000 in the Yoruba-speaking region of southwest Nigeria. All permanent houses have been mapped and assigned numbers by public health workers. Most residents are subsistence farmers or petty traders. Loyola has been engaged in collaborative research with the UCH Dept of Social & preventive Medicine since 1992 and maintains a permanent facility in Igbo-Ora. Ten-thousand adults are being followed in a prospective cohort study on hypertension, and 3,000 family members have been enrolled in genetic studies [123, 124, 126, 127]. Prior studies on EE and obesity have been carried out in this community.

Seychelles – The Republic of Seychelles is an archipelago with 81,000 inhabitants located approximately 1,500 km east of Kenya in the Indian Ocean, and approximately 2,000 km north of the island of Mauritius. Population-based surveys in 1989 and 2004 have shown increasing prevalence of several cardiovascular risk factors in the adult population [146, 147]. The sampling method will be a sex- and age-stratified random sample generated from the national census.

South Africa – Khayelitsha, the 3rd largest township in South Africa, is adjacent to the city of Cape Town. The population is about 500,000 people with 80 percent of the residents living in shacks and 40 percent unemployed. There are no hospitals in Khayelitsha, but there are three community health clinics. Investigators in Cape Town have recently been funded to conduct a population-based 5-year prospective study on AEE and diabetes in 1000 members of this urban community. A sex- and age-stratified random sample will be generated from the national census.

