#### *D.7.1.2 AEE and Weight Change*

The study design contemplates 3 weight determinations over time: one at baseline, a second after 12 months, and a final assessment 2 years after entering the study. To better understand the associations between AEE and body composition, the analysis plan will be carried out in incremental steps corresponding to the degree of sophistication of the statistical methods used.

- 1) Descriptive: Weight change is computed for each subject as the subject's last weight minus baseline weight. The correlation between weight change and AEE will be computed.
- 2) Regression of weight change (as computed above) on AEE will be performed, adjusting for potential confounders of the association.
- 3) AEE will be dichotomized at the median value, resulting in high and low AEE groups. Weight change will be estimated for each individual as the slope of the regression of weight on time (0, 12, and 24 months). Average weight change across AEE groups will be compared. That is, individual regression lines of weight on time will be obtained for each individual, and the average regression among "Low PA" will be compared to the average regression among "High PA" subjects.
- 4) Multilevel analysis (i.e., mixed effect models), which generalizes the previous methods, will be used in our final analysis. This approach will allow for the use of all the available information (i.e., there will be no need to categorize AEE values), thus improving the statistical power [189]. Furthermore, this method allows one to account for the within-subject correlation of the weight determinations and to account (adjust for) subject-specific covariates that may confound the associations. In addition, the dependence of weight change on AEE values can be specifically modeled by the use of random coefficients. Specifically,

$$\text{Level 1: } W_{ij} = \beta_{0i} + \beta_{1i} T_{ij} + \varepsilon_{ij}$$

$$\text{Level 2: } \beta_{0i} = \gamma_0 + \gamma_1 AEE_i + \Omega X_i + \xi_{0i}$$

$$\beta_{1i} = \alpha_0 + \alpha_1 AEE_i + \Psi Z_i + \xi_{1i}$$

$$\varepsilon_{ij} \approx N(0, \sigma^2); \xi_{0i} \approx N(0, \delta_0^2); \xi_{1i} \approx N(0, \delta_1^2); \text{corr}(\xi_{0i}, \xi_{1i}) = \delta_{01}$$

$$\text{corr}(\varepsilon_{ij}, \xi_{0i}) = \text{corr}(\varepsilon_{ij}, \xi_{1i}) = 0$$

$$i = 1, \dots, n; \quad j = 0, 1, 3$$

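### No rule covers pregnancy at the 12- and 24-month visits, so weights taken in pregnancy count as weight change and cannot be identified from the scheduled items

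*Combined protocol and SAP*

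**What the plan says.** The exclusion of "pregnant or lactating women" is a recruitment criterion in D.3.2: "We will exclude individuals with obvious chronic or infectious diseases (including active malaria), pregnant or lactating women, and HIV positive individuals". The cohort is aged 25-45 (D.1.1) and recruited "with equal numbers of men and women" (D.3.2).

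Follow-up carries no matching condition. D.3.1 states: "At 12 and 24 months after the baseline examination, all participants will be recontacted for follow-up clinic examinations". D.2 describes "measuring weight for all 500 participants/site at 12 and 24 months of follow-up", with accelerometry and body composition repeated at 24 months; Table 5 shows the same schedule. Pregnancy history is collected at the initial examination (D.3.1).

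D.7.1.2 first defines weight change as "last weight minus baseline weight", then uses individual slopes and a mixed model over 0, 12 and 24 months. None of these definitions mentions pregnancy.

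Pregnancy comes up again only in D.4.2.3, where women are tested before a DXA scan and pregnant women are excluded. HIV, which is in the same exclusion sentence, is re-tested at follow-up in South Africa because of its effect on body weight (D.3.3, E.2.2).

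**The concern.** Half the cohort are women of childbearing age, followed for two years. Some will probably be pregnant at a follow-up weighing, and the plan then records gestational weight as weight gain, the outcome of Hypothesis 2. The gain under study is modest: the pilot cohorts in C.2.2.2 gained 0.73 and 0.76 kg per year. A small share of women carrying several extra kilograms can therefore be a visible part of the mean.

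Three uses of the data look most exposed:

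- **Change in AEE (D.7.1.2).** The 24-month AEE enters the exposure and the 24-month weight enters the outcome, so a pregnancy at that visit may alter both.
- **BIA at 24 months (D.4.2.2).** Fat and fat-free mass are derived from estimated body water. If pregnancy alters body water (an assumption), the change in body composition is affected as well as weight.
- **Descriptive and between-site weight change.** These are distorted if pregnancy rates differ by site (also an assumption).

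**Working it through.** **1. Does another rule catch these weights?**

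- Outlier rule (D.7.1): it acts beyond 3 SD and keeps values verified as correct. An excess of 5-8 kg lies inside 3 SD of change even if that SD were only 5 kg (3 × 5 = 15 kg), and a true pregnancy weight would be verified.
- Confounders (D.7.1.2): demographic and energy-intake variables are named; pregnancy at follow-up is not.
- Missing-data methods (D.7.4): these weights are observed, so the methods do not apply.
- DXA pregnancy test (D.4.2.3): it governs the scan, not weight, BIA or accelerometry.

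None removes them.

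**2. Shift in the mean.** The documents give neither a pregnancy rate nor a gestational excess. Assume p = 3-8% of women pregnant at a visit and e = 5-8 kg excess.

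- Shift = p × e: 0.03 × 5 = 0.15 kg; 0.08 × 8 = 0.64 kg.
- Expected two-year gain (C.2.2.2): 2 × 0.73 = 1.46 kg and 2 × 0.76 = 1.52 kg, about 1.5 kg.
- Ratio: 0.15/1.5 = 10%; 0.64/1.5 = 43%, in women. Over both sexes the shift in kg halves.

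**3. Added variance in women.** Added variance = p(1 − p)e².

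- Low: 0.03 × 0.97 × 25 = 0.73 kg². High: 0.08 × 0.92 × 64 = 4.71 kg².
- Base variance of change = 2(1 − ρ)SD², with ρ = 0.60 (D.7.2) and SD = 12.5 kg (Nigeria) or 21.6 kg (US) from Table 3: 0.8 × 156.25 = 125 kg²; 0.8 × 466.56 = 373 kg².
- Inflation: 0.73/373 = 0.2% to 4.71/125 = 3.8%.
- If the SD of change were 5 kg (not in the documents): 0.73/25 = 2.9% to 4.71/25 = 18.8%, in women only.

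**4. Bias in the contrast by baseline AEE.** Assume pregnancy at the final visit differs by 2-6 percentage points between the low- and high-AEE halves, with a wider excess of 4-10 kg.

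- Spurious difference over both sexes = difference × excess / 2: 0.02 × 4/2 = 0.04 kg to 0.06 × 10/2 = 0.30 kg.
- In SDs of weight: 0.04/21.6 = 0.002 to 0.30/12.5 = 0.024.
- Design effect in D.7.2: 0.25 SD, or 0.25 × 12.5 = 3.1 kg to 0.25 × 21.6 = 5.4 kg.

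**5. Cost of setting the weights aside.** Per site, 250 women less 20% attrition leaves 200; 3-8% of 200 is 6-16 women, leaving 384-394 of 400 participants.

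The plan's only related figure is 230 per AEE group for 90% power (D.7.2). Its inputs do not reproduce it. Using the Frison-Pocock ANCOVA formula:

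- n = 2(z_α + z_β)²[(1 + ρ)/2 − ρ²]/d², where (1 + 0.60)/2 − 0.36 = 0.44 and d = 0.25.
- Two-sided 5%: 2 × (1.960 + 1.282)² × 0.44/0.0625 = 148 per group. One-sided: 121.
- With 1/0.8 inflation for attrition: 185 or 151.

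D.7.2 does not state sidedness for this calculation. The stated number exceeds what its inputs need, and the present point does not rest on it. On the same inputs (two-sided), power is 0.965 at 200 per group and about 0.96 at 192.

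**The case against.** The best defence is that Hypothesis 2 turns mainly on baseline AEE, which is measured when pregnant and lactating women are excluded. A shift unrelated to baseline AEE adds noise but does not bias that slope. This stands, and step 4 shows that even an assumed imbalance produces little.

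A reader might go further and infer that the error is systematic, because pregnant women move less and fertility differs between sites. The documents say nothing on either, so both remain assumptions. A reader might also infer that outcome variance rises by up to a fifth. That needs a 5 kg SD of change, which the documents do not give, and it holds for women only.

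The defence can also say that Table 5 is not exhaustive: HIV re-testing is required at follow-up but is absent from it. D.2 leaves a detailed protocol to be finalized, and the model in D.7.1.2 can take time-varying covariates. It is therefore too strong to say that affected weights could never be identified. But nothing in these documents schedules the item or tells the analyst what to do with it.

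Finally, weight retained after delivery may be real gain, and the documents give no lactation rate from which to cost its removal. That is a sound reason not to delete lactation visits from the main analysis.

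**Conclusion.** The gap is real. D.3.2 treats pregnancy as a reason not to measure a woman at baseline, and nothing carries that through to 12 and 24 months. As written, gestational weight is counted as weight change.

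On the assumed rates, the mean change in women shifts by 0.15-0.64 kg against about 1.5 kg expected. The effects on variance (about 0.2-4% on the plan's own inputs) and on the baseline-AEE contrast (0.002-0.024 SD against 0.25 SD, on assumed imbalances) are small. The documents do not support reading this as a threat to the main test of Hypothesis 2. The point matters mainly for the change-in-AEE analysis, for BIA change, and for descriptive or between-site weight change if pregnancy rates differ by site. It should be corrected because the remedy is cheap and the status is best captured at the visit.

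**What to change.** - Add to the 12- and 24-month visits a question on current pregnancy, lactation and recent delivery.
- State in D.7.1.2 that weight, BIA and accelerometer values from a visit during pregnancy are set to missing in all change models. The mixed model uses the woman's remaining visits (D.7.4).
- Report two sensitivity analyses: one with all weights included, and one that also sets lactation visits aside.

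The cost is one question per follow-up visit, a sentence or two in the analysis plan, and about 6-16 of 200 women per site at 3-8% pregnant. The lactation analysis would lose more, by an amount the documents do not allow to be estimated; for that reason it is proposed only as a sensitivity analysis.

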#### D.7.1.3 Comparison of Mean AEE Levels Among Sites

The 2 sample t-test will be used to compare means of the primary continuous variables, e.g., BMI, PA, weight, and height. Relevant co-variates will be identified from the within-site analyses and added using multivariable models [186, 190]. We recognize that some modifying factors within sites may not have the same significance across sites, and we will be very careful how variables are chosen for these analyses. Finally, we will test whether the regression slopes of the PA-BMI relationship varies significantly among any pair of sites (i.e., test for interaction).

The association between mean levels of AEE and mean levels of obesity/relative weight will be assessed using regression analysis, following a meta-regression type of approach. That is, mean AEE values will be regressed on mean obesity/relative weight values, weighting by the inverse of the squared standard error of the mean AEE values [191]. This is a widely-used approach in meta-analysis [192]. It is recognized that EI is an important potential confounder of the associations at the individual level. We will estimate the median (and other quantiles of the distribution) usual intake of nutrients (e.g. fat, percent fat) using methods developed by the ISU research group [179, 193] and include them in the meta-regression models.

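### Jamaican participants are to be sampled by district and door to door, but no planned analysis allows for clustering, so Jamaican standard errors and the site comparisons that use them are too optimistic

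*Combined protocol and SAP*

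**What the plan says.** **Sampling (D.3.2).** The general statement is that "the sampling procedures used previously will be employed in the present study". The site descriptions then differ:

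- Jamaica: "Districts were randomly sampled; beginning from a fixed point in each district (e.g., the north-west corner), door-to-door screening took place". This is written about a completed survey; the general statement carries it into the present study.
- US: "We have now contacted individuals on approximately two thirds of the blocks in Maywood and are well known to the community". No rule for selecting people is given.
- Nigeria: "All permanent houses have been mapped and assigned numbers by public health workers". No rule for selecting houses or people is given.
- Seychelles: "The sampling method will be a sex- and age-stratified random sample generated from the national census".
- South Africa: "A sex- and age-stratified random sample will be generated from the national census".

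**Analysis (D.7.1).** D.7.1.1 lists Pearson, Spearman and Lin coefficients, Fisher's Z, bootstrap intervals, permutation tests and linear regression. For site means, D.7.1.3 states: "The 2 sample t-test will be used to compare means of the primary continuous variables, e.g., BMI, PA, weight, and height". The same section regresses site means on one another, weighting by the inverse squared standard error of mean activity energy expenditure (AEE).

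**Correlation that is allowed for.** The mixed model in D.7.1.2 handles repeated weights within a person and may include site factors. D.7.4 mentions correlation within a participant. D.7.2 uses an effective sample size of 7 instead of 10 sex-by-country means, for power only. District and household appear nowhere in D.7.

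**The concern.** People canvassed along the same streets tend to share income, work, food supply and walking environment, so their AEE and BMI are likely to be positively correlated. A standard error computed as if 500 Jamaicans were drawn independently is then too small. Three planned results inherit the error: confidence intervals for Jamaican means, the t-tests of Jamaica against other sites, and Jamaica's weight in the meta-regression. A bootstrap or permutation test that resamples individuals repeats it. Because two other sites describe census samples without area clusters, precision would be overstated at one site relative to others.

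The timing matters too. If district and household are not recorded at enrolment, the clustering may be hard to correct later.

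**Working it through.** **1. Do the plan's own figures contain a design effect?** D.7.2 gives power for a one-sided comparison of correlations, 150 against 150. Alpha is not stated there; I take the 5% stated for hypothesis 1. With independent participants,

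power = Φ( |atanh r₁ − atanh r₂| / √(1/147 + 1/147) − 1.645 ), where the square root is 0.1166.

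| Correlations | Difference in Z | Power | Stated |
|---|---|---|---|
| −0.40 vs −0.65 | 0.7753 − 0.4236 = 0.3517 | 91.5% | over 91% |
| −0.45 vs −0.65 | 0.7753 − 0.4847 = 0.2906 | 80.1% | over 80% |
| −0.35 vs −0.60 | 0.6931 − 0.3654 = 0.3277 | 87.8% | greater than 85% |

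All three agree with a design effect of 1. The second leaves almost no room for another value: a design effect of 1.04 at just one of the four sites gives 79.8%.

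**2. Design effect for a Jamaican mean.** Inputs: 500 per site (D.3.2). *Assumed*, because the documents give neither: m = 5 to 20 people per district and ICC = 0.01 to 0.05. Formulas: DEFF = 1 + (m − 1) × ICC; the standard error is multiplied by √DEFF; effective n = 500/DEFF.

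**3. True size of a nominal 5% t-test of Jamaica against an unclustered site.** With equal n and SD, the true variance of the difference is (DEFF + 1)/2 times the planned one. The size is therefore 2 × [1 − Φ(1.96 / √((DEFF + 1)/2))].

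| m | ICC | DEFF | SE multiplier | Effective n | True size |
|---|---|---|---|---|---|
| 5 | 0.01 | 1.04 | 1.02 | 481 | 5.2% |
| 5 | 0.05 | 1.20 | 1.10 | 417 | 6.2% |
| 10 | 0.05 | 1.45 | 1.20 | 345 | 7.7% |
| 20 | 0.01 | 1.19 | 1.09 | 420 | 6.1% |
| 20 | 0.05 | 1.95 | 1.40 | 256 | 10.7% |

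**4. Meta-regression weight.** With five sites of equal SD, Jamaica's planned share is 1/5 = 20%. With a correct standard error it is (1/DEFF)/(1/DEFF + 4): 19.4% at DEFF 1.04 and 11.4% at DEFF 1.95.

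**5. How much the ecological regression depends on this.** Weight-adjusted AEE for men in Table 1 is 1094, 985, 761, 866 and 1011 kcal/d, a between-site SD of about 131. Assuming 250 men per site, Jamaica's standard error is 271/√250 = 17.1, or 17.1 × 1.40 = 23.9 at DEFF 1.95. Spread between sites dominates either way.

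**6. Correlations in the doubly labeled water subset.** If only Jamaica is clustered, applying the design effect of a mean to its 75 participants lowers the 91.5% to 91.2% at DEFF 1.04 and 87.4% at DEFF 1.95. This is a rough and probably pessimistic bound. The subset is random, so 75/500 = 15% of 20 people is about 3 per district, and DEFF is then only 1 + 2 × 0.05 = 1.10.

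**The case against.** The strongest reply is that this is one site out of five, that the inputs are assumed, and that the main hypotheses hardly move.

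- **Scope.** This stands. A reader might infer that every site mean and every between-site test is affected. The documents do not support that. The Seychelles and South African samples are stratified census samples with no area clusters described. The US sentence reports how far past contact has reached and does not set a block-by-block sampling rule. The Nigerian house map is a frame from which houses could be drawn at random. Error rates that need two clustered sites therefore have no documentary basis.
- **Independence everywhere.** It would be wrong to say that the plan ignores all correlation: the mixed model handles repeated weights, and the effective sample size of 7 handles sex-by-country means. Neither reaches districts or households.
- **Size.** This stands. With many districts and few people in each, the effect is slight.
- **Hypotheses.** This largely stands. Hypotheses 1 and 2 concern correlations and slopes, which are less affected than means. Hypothesis 3 is a regression on 5 or 10 points, dominated by spread between sites. D.7.2 also offers a comparison of the groups with most and least obesity. By the population BMIs in Table 1 these are Maywood and Nigeria for both sexes, so Jamaica is not involved.

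None of this supplies the missing term. The area design is carried forward for Jamaica, and the planned t-tests and weights use its standard error.

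**Conclusion.** The point holds for Jamaica. Its area sample is to be reused, and no planned analysis accounts for districts or households. With a positive ICC, the standard errors of Jamaican means, the t-tests of Jamaica against other sites, and Jamaica's inverse-variance weight are too optimistic.

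The range of 5.2% to 10.7% for the true size of the t-test rests on the assumed 5 to 20 people per district and ICC of 0.01 to 0.05, equal n and SD, and an unclustered comparison site. The direction needs only a positive ICC; the size cannot be found from the documents.

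For the US and Nigeria the gap is different: the selection rule is not stated, so clustering can be neither asserted nor excluded. The main conclusions on within-site associations and the ecological slope are unlikely to turn on this. Comparisons of the Jamaican mean with other sites could.

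**What to change.** 1. State the selection rule for each site in D.3.2. For Jamaica, add the number of districts and the planned number of people per district.
2. Record district and household ID at enrolment in Jamaica and at any other site that samples by area or house.
3. At those sites, use cluster-robust standard errors, with a small-sample correction if districts are few, or a district random intercept. Sites that draw individuals from a census need no such term.
4. Use the resulting design-based standard error in the D.7.1.3 t-tests and meta-regression weights.
5. Resample districts, not individuals, in the bootstrap and permutation tests at those sites.

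Limiting enrolment to one adult per household is not proposed. Selection probability would then depend on household size, and site means would need weights.

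**Cost:** two extra form fields, a modest addition to the analysis code, and somewhat wider intervals at the clustered sites.
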